#### 3.4. NUMBER OF CENTRES

The cardiac rehabilitation center at Prince of Wales Hospital (POWH).

#### 3.5. DURATION

It is estimated that more than 350 patients attend the cardiac rehabilitation unit at POWH every year with an estimated 29 patients per month. Based on the recruitment criteria, the anticipation that not all patients will agree to participate and that the rate of recruitment must be manageable for the researcher, recruitment duration is estimated to take up to six months to recruit 28 participants. Hence, the duration of the study will be approximately six months for recruitment and a six months intervention and follow-up period.

#### 4. PARTICIPANT SECTION

#### 4.1. INCLUSION CRITERIA

- 1) 18 years of age or older;
- 2) Established diagnosis of cardiac disease by their physician and referred to the cardiac rehabilitation program at POWH;
- 3) Prescribed at least one cardio-protective medication at least 7 days prior to recruitment;
- 4) They must have primary responsibility for taking their medications themselves (i.e. whilst a carer may play a role in supporting or prompting medication taking, they should not be identified as being accountable for ensuring the patient's adherence to their medication schedule);

Version 2: 20/05/2016 ----- Page 11 of 42

- 5) Participants must be able to speak, read and understand English, own a personal mobile phone, and be able to receive and reply to phone calls and text messages;
- 6) They must be willing to give written or oral informed consent to participate to in the study.
- 7) To be eligible for the trial phase, patients must be identified with at least one medication non-adherence factor, indicated by results of the medication adherence questionnaire and responses to the interview questions.

[figure not shown]
#### 4.2. EXCLUSION CRITERIA

Patients who are deaf, blind or unable to accept phone calls will be excluded. Those clinically judged with cognitive impairment that limits their ability to understand and answer study questions will be excluded.

Version 2: 20/05/2016 ----- Page 12 of 42

#### 5. STUDY OUTLINE

#### 5.1. STUDY FLOW CHART

Version 2: 20/05/2016 ----- Page 13 of 42

#### 5.2. INVESTIGATION PLAN

Interventions	Enrolment Visit	Visit 1	Visit 2	Telephone call or home visit
Screen for Inclusion / Exclusion criteria	✓			
Informed Consent	✓			
Survey	✓			√
Semi-structured interview		✓		
Motivational interviewing			✓	

Patients referred to the cardiac rehabilitation at POWH are routinely booked for a 6 week cardiac rehabilitation (CR) program, delivered during one session per week. The enrolment visit, visit 1 and visit 2 of the study will occur during times when the participant is booked to attend CR.

The final data collection point will occur at 6 months post recruitment. Participants will be asked to agree a convenient time when they can complete the questionnaire by telephone or by home visits from the researcher.

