#### 3.2. STUDY GROUPS

Participants will be cardiac patients referred to a cardiac rehabilitation program following their hospital admission for acute cardiac events; those participating in the pilot trial phase will be randomly allocated to receive either the intervention plus usual care or usual care only.

Version 2: 20/05/2016 ------ Page 9 of 42

**Intervention group:** Participants in the intervention group will receive usual care plus behavioural counselling about medication adherence using MINT techniques and text message reminders. Each patient will receive approximately 30-40 minutes of a single MINT counselling session following recruitment (Appendix D) (Ma et al., 2014). The core of motivational interviewing is for the counsellor to be simultaneously sympathetic and supportive, as well as directive in moving patients toward change by strengthening their own reasons for change (Levensky et al., 2007). As part of the MINT counselling, the researcher has the opportunity to provide information that the patient may need or to explore some of the barriers that keep this patient from adherence to medications (Dart, 2010). Text message reminders (TM) (Appendix E) will be sent to these participants: one text message daily for two weeks, then on alternate days for two weeks and then on a weekly basis for the next 6 months (Wald et al., 2014). The content of the text message reminders will vary according to the patients' non-adherence factors. An example of the text message reminder is:

The researchers will use a structured MINT counselling script (Appendix D) designed for patients with low adherence to medications, with each session tailored to the medication adherence characteristics of the individual patient (Dart, 2010). All MINT sessions will be audio taped and reviewed by a clinician qualified in MINT to ensure fidelity to the technique (Ma et al., 2014).

**Control group**: Patients randomised to the control group will receive standard care alone for the study period. They will be contacted at baseline and 6 months to complete the same measurements and interviews as the intervention group.

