#### **5.3.1.** Phase one (Quantitative Exploratory survey)

**Sample and sampling approach**: The method of consecutive sampling will be used. This technique involves selecting all eligible participants who agree to participate, provided they meet inclusion criteria, until a desired number of participants has been recruited (Schuster and Powers, 2005). The survey sample will be selected as a consecutive cohort of patients referred to cardiac

Version 2: 20/05/2016 ----- Page 14 of 42

rehabilitation for cardiac disease secondary prevention. Cardiac patients eligible to participate will be identified by the Clinical Nurse Consultant in Cardiac Rehabilitation as they attend for their first session of cardiac rehabilitation. Those interested will be referred to the researcher, who will explain the survey (phase one) and the semi-structured interview (phase two) and will provide them with an information statement sheet and consent form. These two study phases will identify patients who are non-adherent with at least one cardiac medication who will be eligible to participate in the pilot trial phase (phase three). The survey and semi structured interviews will also identify factors that impact on the patients' adherence to cardiac medications.

Questionnaire Instrument: The instrument consists of a number of questionnaires to gather data about medication adherence, patient behaviours, beliefs and other factors associated with medication non-adherence (Appendix A). The questionnaires will be paper based, self-administered, simple and easy to complete, and suitable for participants with low literacy skills. Data collected will include demographic data: age, gender, marital status, social background (next of kin/ carer), home domicile situation, level of education, literacy, and ethnicity / country of birth; and clinical data: disease diagnosis and co-morbidities (Appendix B). Medication practices will be explored using the following instruments:

- Medication Adherence Questionnaire (Morisky et al., 1986).
- Adherence to Refills and Medications Scale (Kripalani et al., 2009).
- Belief about Medicine Questionnaire (Horne et al., 1999).
- Medication Adherence Self-Efficacy Scale-Revised (Fernandez et al., 2008).
- Medication Specific Social Support (Lehavot et al., 2011).

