Medication Adherence Self-Efficacy	Medication Adherence Self- Efficacy Scale-Revised (MASER- R)	13 items scale.     assess individual's judgment of their ability to adhere to medications under a variety of challenging situations	MASES-R assessed against electronic medication adherence & correlated positively & significantly.	Cronbach's α =0.91
Social Support	Medication Specific Social Support (MSSS)	●8-item survey ■ identify how often others may have helped patients with their therapy. ■ 4 point Likert scale.	Not stated	Cronbach's α = 0.92

**Survey procedure:** Participants will be asked to complete the paper-based survey instrument when they attend cardiac rehabilitation; they will be encouraged to complete it whilst they are at the hospital and to deposit it into a provided box in the cardiac rehabilitation venue. Participants can also complete the survey questionnaires at home and post it back via mail using the enclosed prepaid envelope if they prefer. The survey instrument will be printed in large font size and formatting for easy reading by older participants.

Version 2: 20/05/2016 ----- Page 17 of 42

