#### 7. BLINDING AND UNBLINDING

Neither participants nor researcher can be blinded to the group allocation of participants (intervention or usual care only groups).

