# **Appendix (E): The text message (TM) reminder content**

# Week 1-2 Text message sent DAILY Week 3-4 Text message sent on ATERNATE DAYS Weeks 5+ Text message sent weekLY Text message sent on ATERNATE DAYS Text message sent on ATERNATE DAYS Text message sent weekLY

**6 MONTHS** 

Text message reminders (TM) will be sent to these participants one text message daily for two weeks, then alternate day texts for two weeks and then weekly texts for the next 6 months. The content of the text message reminders will vary according to the patients' non-adherence factors. An example of the text message reminder is:

Non-responders or patients who reply back 'No' in response to the message will receive a telephone call from the researcher, to determine whether the patient is experiencing problems taking or refilling their medication, and resolve this if possible (e.g. the patients has difficulty accessing the pharmacy). If the patient mentioned experiencing side-effects from medications, the researcher will advise the patient to make an appointment with their GP or consulted with their pharmacist. If researcher cannot contact the patient by telephone, a letter will be sent to their home address informing them that the researcher has been unable to contact them by telephone and asking them to contact the study team.

Version 2: 20/05/2016 ------ Page 42 of 42

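### The 6-month self-report is collected by a role that, on the natural reading, is unblinded and counsels only the intervention arm, so reporting bias is likely to favour the intervention

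*Protocol*

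**What the plan says.** **Baseline.** Protocol 5.3.1 describes the survey in these terms: "The questionnaires will be paper based, self-administered, simple and easy to complete, and suitable for participants with low literacy skills". Participants are encouraged to finish it at the hospital and "deposit it into a provided box in the cardiac rehabilitation venue", and the same section adds: "Participants can also complete the survey questionnaires at home and post it back via mail using the enclosed prepaid envelope if they prefer". No interviewer stands between the participant and the form.

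**Six months.** Section 5.2 places the last data collection at 6 months after recruitment: "Participants will be asked to agree a convenient time when they can complete the questionnaire by telephone or by home visits from the researcher". Section 3.2 has controls complete the same measurements at the same time points.

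**The researcher's other tasks.** Section 3.2 says: "As part of the MINT counselling, the researcher has the opportunity to provide information that the patient may need". It also says, in the plural, "The researchers will use a structured MINT counselling script (Appendix D"). Appendix E adds that intervention participants who do not answer a text, or who answer No, "will receive a telephone call from the researcher, to determine whether the patient is experiencing problems taking or refilling their medication".

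**Blinding.** Section 7: "Neither participants nor researcher can be blinded to the group allocation of participants". No separate outcome assessor is described.

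**Outcome and tests.** Sections 2.2 and 9 make adherence at 6 months, or its change from baseline, the trial's primary outcome. Section 9 compares questionnaire scores between arms with independent-samples t-tests and within arms with paired t-tests. No pill count, refill record or other objective measure of adherence is planned.

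**The concern.** The MAQ asks people to admit that they forget, are careless with, or stop their medicines. Such answers are open to social desirability, and the pull is stronger when they are given to someone who has invested in the participant's improvement.

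By 6 months an intervention participant has had a counselling session that, in the Appendix D example, goes over their own survey results and praises their effort. They have also had months of texts and possibly telephone calls about taking and refilling medicines. Controls have had none of this. If the same role then collects the answers, the arms can differ in reported adherence with no difference in medicine taking. The planned t-test cannot separate the two, and no objective measure is there to do so.

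The change from paper to telephone or home visit is a second and separate problem. It can move scores in both arms between baseline and 6 months, and a paired test would read that as change in behaviour.

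**Working it through.** **1. Is the collector independent of the intervention?** Section 5.2 names the researcher for home visits. Section 3.2 has the researcher counselling, Appendix E has the researcher telephoning the texted participants, and section 7 has the researcher unblinded. The contacts specific to one arm are the counselling session, the texts and the follow-up calls. Appendix E runs weekly texts for 6 months after four weeks of denser texting, so this contact can still be active when the outcome is collected.

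**2. What the change of mode does.** Let m be a shift caused by the mode and common to both arms, and b an extra reporting shift in the intervention arm only.
- Between-arm difference at 6 months, or in change from baseline: (effect + b + m) − m = effect + b. The mode shift cancels.
- Change within an arm: m stays in. The paired t-tests are exposed to it in both arms.

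**3. The plan's own figure.** Section 8: n = 2 × (1.96 + 0.842)² × 3.285² / 4.42² = 169.448 / 19.5364 = 8.67, so 9 completers per arm. This reproduces. The 28 recruited at 1:1 make 14 per arm. Both sizes are used below.

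**4. Size of b.** The documents give none, so this is an assumed scenario: 10-30% of intervention participants change one MAQ answer from yes to no, and the SD of the MAQ total (range 0-4) is 1.1-1.3.
- Shift in the mean: 0.10 × 1 = 0.1 to 0.30 × 1 = 0.3 points.
- In SD units: 0.1 / 1.3 = 0.08 to 0.3 / 1.1 = 0.27.

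**5. Between-arm false positives.** With no true effect, the two-sided 5% t-test statistic follows a noncentral t distribution with 2n − 2 degrees of freedom and noncentrality b × √(n/2), with b in SD units.

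| Per arm | b (SD) | Noncentrality | Rejection rate |
|---|---|---|---|
| 14 | 0.08 | 0.20 | 5.4% |
| 14 | 0.27 | 0.72 | 10.7% |
| 9 | 0.08 | 0.16 | 5.3% |
| 9 | 0.27 | 0.58 | 8.5% |

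As a sensitivity case outside this scenario, b = 0.5 SD gives 24.7% with 14 per arm and 17.0% with 9.

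**6. Within-arm false positives.** For a common mode shift c (in SD units) and a correlation r between baseline and 6 months, the paired test has noncentrality c × √n / √(2(1 − r)). Taking c = 0.5 and r = 0.3 to 0.7, both assumed, the rejection rate with no true change is 20% to 40% with 9 per arm and 31% to 61% with 14.

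**The case against.** **The mode change cannot explain a between-arm bias.** A reader might infer that moving from paper to telephone or home visit itself favours the intervention. It does not: controls make the same move, and the shift cancels between arms. This objection stands in full. The between-arm risk rests only on who collects the answers.

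**The text does not say that one person counsels and assesses, or that answers are spoken.** Section 5.2 ties the researcher to home visits and does not say who telephones. A participant could fill in the paper form by hand during a visit, and section 3.2 uses the plural for those delivering the script. This stands as a limit on certainty. Even so, no other assessor is named, and telephone completion cannot be self-completion on paper.

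**Controls also know the researcher.** Before randomisation every trial participant has a face-to-face interview with the researcher about medicine taking (section 5.3.2), and contradictions between survey and interview are put back to the participant (section 9). So baseline is not free of the researcher's influence. This narrows the contrast without closing it: the excess in the intervention arm is one session of 30-40 minutes, the texts and any calls.

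**Personal collection protects follow-up.** With attrition of up to 50% allowed for, telephone or home collection is a defensible way to keep data, and a posted form may not come back. This is a real trade-off, and the fix has to keep a fallback.

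**Conclusion.** The point holds as a likely bias, not a demonstrated one. Blinding of participants and counsellor is out of reach, as section 7 says, but that does not require the counselling role to collect the outcome. On the natural reading it does so here, for a wholly self-reported outcome, and the expected direction favours the intervention.

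The size cannot be estimated from the documents. Under the stated assumptions the inflation of the 5% error rate is modest: about 5.4%-10.7% with 14 per arm and 5.3%-8.5% with 9. The larger figures in the working need a 0.5 SD shift, which nothing in the documents supports as likely.

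The change of mode is a separate fault that affects change from baseline within each arm and the paired t-tests. A within-arm improvement should not be read as an effect while the mode differs between the two time points.

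**What to change.** In sections 5.2 and 3.2, state that at 6 months:
- both arms self-complete the same paper survey as at baseline and return it sealed in the prepaid envelope; if a home visit is needed, the participant completes the form and seals it;
- the researcher's contact is limited to prompting return;
- telephone completion is kept only as a fallback for forms not returned, is offered in the same way in both arms, and the mode is recorded and reported by arm.

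This restores the baseline mode and takes the counselling role out of the answering. It costs postage and wording and needs no extra staff, because the form and the envelope are already in the protocol.

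The downside is some risk of non-return and of mixed modes, possibly unequal between arms; the fallback limits the first and the reporting by arm shows the second. Participants stay unblinded and those counselled know that their survey answers are read, so the bias is reduced and not removed.

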#### 5.3. STUDY PROCEDURE

This study will be conducted in accordance with ethical standards established by the Australian Research Council and the National Health and Medical Research Council (National Health and Medical Research Council, 2015). Recruitment will occur under the supervision of the Clinical Nurse Consultant for cardiac rehabilitation with the agreement of the director of nursing and the cardiology consultant.

#### **5.3.1.** Phase one (Quantitative Exploratory survey)

**Sample and sampling approach**: The method of consecutive sampling will be used. This technique involves selecting all eligible participants who agree to participate, provided they meet inclusion criteria, until a desired number of participants has been recruited (Schuster and Powers, 2005). The survey sample will be selected as a consecutive cohort of patients referred to cardiac

Version 2: 20/05/2016 ----- Page 14 of 42

rehabilitation for cardiac disease secondary prevention. Cardiac patients eligible to participate will be identified by the Clinical Nurse Consultant in Cardiac Rehabilitation as they attend for their first session of cardiac rehabilitation. Those interested will be referred to the researcher, who will explain the survey (phase one) and the semi-structured interview (phase two) and will provide them with an information statement sheet and consent form. These two study phases will identify patients who are non-adherent with at least one cardiac medication who will be eligible to participate in the pilot trial phase (phase three). The survey and semi structured interviews will also identify factors that impact on the patients' adherence to cardiac medications.

Questionnaire Instrument: The instrument consists of a number of questionnaires to gather data about medication adherence, patient behaviours, beliefs and other factors associated with medication non-adherence (Appendix A). The questionnaires will be paper based, self-administered, simple and easy to complete, and suitable for participants with low literacy skills. Data collected will include demographic data: age, gender, marital status, social background (next of kin/ carer), home domicile situation, level of education, literacy, and ethnicity / country of birth; and clinical data: disease diagnosis and co-morbidities (Appendix B). Medication practices will be explored using the following instruments:

- Medication Adherence Questionnaire (Morisky et al., 1986).
- Adherence to Refills and Medications Scale (Kripalani et al., 2009).
- Belief about Medicine Questionnaire (Horne et al., 1999).
- Medication Adherence Self-Efficacy Scale-Revised (Fernandez et al., 2008).
- Medication Specific Social Support (Lehavot et al., 2011).

Non-adherence to medications will be assessed by the **Medication Adherence Questionnaire** (**MAQ**) designed to measure medication adherence behaviour and barriers such as forgetfulness, carelessness, adverse effects and efficacy. MAQ includes simple four-item dichotomous questions, scoring one point for each yes response; total scores are categorised as: 0 point indicating high; 1-2 points medium, and 3-4 points low medication adherence behaviour.

The Adherence to Refills and Medications Scale (ARMS) will be used to determine the patient medication adherence behaviour in terms of self-regulation. The ARMS comprises a 12-item scale with the first 8-item medication taking subscale assessing correct self-administration ability for the prescribed regimen. The next 4-item prescription refill subscale assesses the patient's ability to refill medications on schedule. Each item is scored on a four point scale ranging from l=

Version 2: 20/05/2016 ----- Page 15 of 42

none of the time to 4= all the time. The higher numbers on the scale demonstrate patient's better ability to refill medications on schedule.

The Belief about Medicine Questionnaire (BaMQ) elicits information on patients' beliefs about their medicines where they may relate to adherence. It identifies whether the patient holds beliefs that their medicines are necessary or if they have concerns about their medicines. The study will use the short version of the BaMQ (the 8-item) developed by Horne et al., 1999. This version is composed of four subscales containing two items each, and assessing: General Harm; General Overuse; Specific Necessity; and Specific Concerns. Respondents indicate their degree of agreement with each statement on a five point Likert scale, ranging from l=strongly disagree to 5=strongly agree. The lower numbers on the scale demonstrate the patient's strong beliefs about taking medications. Scores are summed to give a total score, with higher scores indicating more positive beliefs. The focus of the BaMQ, is identification of barriers to medication adherence, contributing to comprehensive evaluation of the drivers behind medication adherence.

The Medication Adherence Self-Efficacy Scale-Revised (MASES-R) consists of 13 items that evaluate an individual's judgment of their ability to adhere to prescribed medications under a variety of challenging situations. Twelve of the items ask about patient confidence in taking medications in specific situations (e.g. busy at home, no symptoms, traveling), and one item addresses confidence in ability to make medication adherence as part of daily routine. Each item is scored on a four point scale, ranging from: 0= Not at all sure, 1= A little sure, 2= Fairly sure, and 3= Extremely sure. A single scale score is presented, the mean of all item scores. Higher scores on the scale indicate higher confidence.

The **Medication Specific Social Support** (MSSS) is an 8-item survey of medication-specific social support to identify how often others may have helped patients with their therapy, with scored for each item ranging from 0 (never) to 4 (very often). A single mean score is presented of medication-specific index of support.

These instruments have demonstrated rigor; see Table 1.

Version 2: 20/05/2016 ----- Page 16 of 42

Table 5: The reliability and validity of the selected study instruments

Concept	Name of Questionnaire	Number of Items	Validity Test	Reliability Test Score
Medication Adherence behaviours & barriers	Medication Adherence Questionnaire (MAQ)	Four-item questionnaire measure medication adherence behaviour specifically, barriers such as; forgetfulness and carelessness, & adverse effects & efficacy	Validated in patients with hypertension, dyslipidaemia, heart failure, and CAD	Cronbach's α= 0.61
Medication Adherence Behaviour (Self- Regulation)	Adherence to Refills and Medications Scale (ARMS)	12-item scale.     The first 8-item medication taking subscale assess correct self-administer prescribed regimen ability.     The next 4-item prescription refill subscale assesses a patient's ability to refill medications on schedule	Validated in patients with CAD & other chronic diseases	Cronbach's α = 0.81
Medication taking beliefs	Belief about Medicine Questionnaire (BaMQ)	●8-item short version.  ● The 4-BaMQ subscales are containing two items each includes: General Harm; General Overuse; Specific Necessity; & Specific Concerns on a five point Likert scale.	BaMQ significantly correlated with other adherence scales: MAQ, Morisky Medication Adherence Scale (MMAQ), & medication adherence rating scale (MARS-5)	Cronbach's α = 0.70
Medication Adherence Self-Efficacy	Medication Adherence Self- Efficacy Scale-Revised (MASER- R)	13 items scale.     assess individual's judgment of their ability to adhere to medications under a variety of challenging situations	MASES-R assessed against electronic medication adherence & correlated positively & significantly.	Cronbach's α =0.91
Social Support	Medication Specific Social Support (MSSS)	●8-item survey ■ identify how often others may have helped patients with their therapy. ■ 4 point Likert scale.	Not stated	Cronbach's α = 0.92

**Survey procedure:** Participants will be asked to complete the paper-based survey instrument when they attend cardiac rehabilitation; they will be encouraged to complete it whilst they are at the hospital and to deposit it into a provided box in the cardiac rehabilitation venue. Participants can also complete the survey questionnaires at home and post it back via mail using the enclosed prepaid envelope if they prefer. The survey instrument will be printed in large font size and formatting for easy reading by older participants.

Version 2: 20/05/2016 ----- Page 17 of 42

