#### **APPENDICES**

# **Appendix (A) Medication Adherence Questionnaires**

Situations come up that make it difficult for people to take their medications as prescribed by their doctors. Below is a list of such situations. We want to know your opinion about taking your cardiac medication(s) under each of them. Please indicate your response by checking the box that most closely represents your opinion.

Questions	Yes	No
1. Do you ever forget to take your medicine?		
2. Are you careless at times about taking your medicine?		
3. When you feel better do you sometimes stop taking your medicine?		
4. Sometimes if you feel worse when you take your medicine, do you stop taking it?		

Questions	None of the time	Some of the time	Most the time	All the time
5. How often do you forget to take your medicine				
6. How often do you decide not to take your medicine?				
7. How often do you forget to get prescriptions filled				
8. How often do you run out of medicine?				

Version 2: 20/05/2016 ------ Page 28 of 42

9. How often do you skip a dose of your medicine before you go to the doctor?		
10. How often do you miss taking you medicine when you feel better?		
11. How often do you miss taking your medicine when you feel sick?		
12. How often do you miss taking your medicine when you are careless?		
13. How often do you change the dose of your medicines to suit your needs (like when you take more or less pill than you're supposed to)?		
14. How often do you forget to take your medicine when you are supposed to take it more than once a day?		
15. How often do you put off refilling your medicines because they cost too much money?		
16. How often do you plan ahead and refill your medicines before they run out		

There are no right or wrong answers. For each of the situations listed below, please rate how sure you are that you can take your cardiac medications all of the time.

How confident are you that you can take your cardiac medications:	Not at all sure	A little sure	Fairly sure	Extremely sure
17. When you're busy at home				
18. When there is no one to remind you				
19. When you worry about taking them for the rest of your life				
20. When you do not have any symptoms				
21. When you are with family members				
22. When you are in a public place				
23. When the time to take them is between your meals				
24. When you are travelling				
25. When you take them more than once a day				
26. When you have other medications to take				

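### The protocol says a higher ARMS score means better adherence, but 11 of the 12 printed items score lapses and the one positively worded item is not reversed

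*Protocol*

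**What the plan says.** Protocol section 5.3.1 describes ARMS in four statements.

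- Taking items: "The ARMS comprises a 12-item scale with the first 8-item medication taking subscale assessing correct self-administration ability for the prescribed regimen".
- Refill items: "The next 4-item prescription refill subscale assesses the patient's ability to refill medications on schedule".
- Coding: each item has four points, where 1 to 4 runs from "none of the time to 4= all the time". No item is marked for reverse coding, and the text does not say whether the items are summed or averaged.
- Direction: "The higher numbers on the scale demonstrate patient's better ability to refill medications on schedule".

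Appendix A prints the 12 ARMS items as numbers 5 to 16. The first two are "5. How often do you forget to take your medicine" and "6. How often do you decide not to take your medicine". The last is "16. How often do you plan ahead and refill your medicines before they run out".

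Section 9, under the pilot trial phase, lists ARMS among the questionnaire scores to be compared between arms by an independent-samples t-test and within arms by a paired t-test.

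**The concern.** The direction sentence and the printed items contradict each other. A patient who always forgets, always skips doses and always runs out collects the high numbers that section 5.3.1 describes as good. Applied literally, the rule would describe an arm whose adherence improves, and whose ARMS score therefore falls, as getting worse.

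This matters because ARMS and the Medication Adherence Questionnaire (MAQ) are the two instruments in the battery that measure adherence behaviour itself. The MAQ gives one point per admitted lapse, so higher is worse there too. With ARMS read in the opposite sense, the two scales would seem to disagree when they agree.

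Item 16 is a separate problem. Added in without reversal, it pulls against the other 11 items whichever direction is declared.

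**Working it through.** **Inputs.** Coding 1 to 4 and the stated direction: section 5.3.1. Item wording: Appendix A, items 5 to 16. Use of the score: section 9. Assumption: the total is a sum. If it is a mean, divide the totals by 12.

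**Step 1: item counts.** Classified by content, the taking items are 5, 6 and 9 to 14 (8 items) and the refill items are 7, 8, 15 and 16 (4 items). 8 + 4 = 12, which reproduces the protocol's counts.

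**Step 2: direction of each item.** Items 5 to 15 ask about forgetting, deciding against a dose, running out, skipping, missing, altering the dose, or delaying a refill because of cost. On all 11, a 4 is the worst answer. On item 16, a 4 is the best answer.

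**Step 3: extreme patients, coded as written.**

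- Fully adherent: 11 × 1 + 4 = 15 (mean 15/12 = 1.25).
- Fully non-adherent: 11 × 4 + 1 = 45 (mean 45/12 = 3.75).

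The non-adherent patient is 30 points higher, and the stated rule calls that better.

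**Step 4: does the sentence hold if it covers only the refill items?** It mentions refilling, so this needs checking. On items 7, 8, 15 and 16:

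- Perfect refiller: 1 + 1 + 1 + 4 = 7.
- Worst refiller: 4 + 4 + 4 + 1 = 13.

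The sentence is still backwards.

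**Step 5: reverse item 16 (5 minus the response).**

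| Score | As written: adherent / non-adherent | Width | Item 16 reversed: adherent / non-adherent | Width |
|---|---|---|---|---|
| Total, 12 items | 15 / 45 | 30 | 12 / 48 | 36 |
| Refill items by content | 7 / 13 | 6 | 4 / 16 | 12 |
| Taking items by content | 8 / 32 | 24 | 8 / 32 | 24 |

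**Step 6: which error alters the test?** Reversing all 12 items turns a total S into 12 × 5 − S = 60 − S. The standard deviation and the size of the difference stay the same, and only the sign of t changes. The two-sided p-value is therefore unaffected by direction alone.

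Item 16 is different. Let A be the sum of items 5 to 15 and y the response to item 16. The raw total is A + y and the consistent total is A + (5 − y), so they differ by 2y − 5. That is −3 at y = 1 and +3 at y = 4. The shift varies between patients, so it changes the data entering both t-tests.

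**The case against.** Several arguments limit the point.

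**Item reversal belongs in a scoring manual or analysis plan.** This is fair for item 16 taken alone, since ARMS is a cited published instrument. It does not cover the direction sentence, which is an explicit statement in the protocol that the protocol's own items contradict. A separate plan could settle the scoring, but this sentence would still need correcting.

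**The effect on inference is small.** Much of this stands. Direction alone leaves p-values unchanged, item 16 is one of 12 items, and an analyst who looked at the items might notice the problem. Trial eligibility is decided on the MAQ (section 5.4), so who is randomised does not depend on ARMS. The sample-size arithmetic does not depend on it either.

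**A reader might infer that the primary outcome is inverted.** Sections 2.2 and 9 give the outcome as adherence at six months and change in scores, without naming a scale. The planned difference of 4.42 points is larger than the MAQ's 0 to 4 range, which may suggest ARMS. But that figure is taken from a cited study of motivational interviewing in hypertension care, and nowhere does the protocol name ARMS as primary.

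**A reader might infer that the subscales are split wrongly.** Read as item positions, the first eight would include refill items 7 and 8, and the last four would include taking items 13 and 14. The words can equally mean the first and the second subscale. The 8 and 4 counts are right by content, and section 9 plans no subscale analysis. This is a matter of wording only.

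**A reader might say that the worst patient is scored as best.** That goes slightly too far: the coded maximum is 48, so 45 is near the top but not at it.

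**Conclusion.** The stated ARMS direction is wrong as written. It contradicts 11 of the 12 items in Appendix A, and it remains wrong if confined to the refill items. This follows from the protocol's text alone.

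There are two distinct effects. The direction error reverses how the between-arm and within-arm ARMS results would be read and leaves two-sided p-values intact. The unreversed item 16 shifts individual totals by up to 3 points either way. It also shortens the distance between full adherence and full non-adherence from 36 points to 30, and from 12 to 6 on the refill items. The point figures assume summed items; with a mean the direction finding is the same.

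This should be fixed but does not threaten the trial: ARMS is not named as the primary outcome, eligibility rests on the MAQ, and responses already collected can be rescored.

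**What to change.** State one direction in section 5.3.1 and use it in section 9. Either convention works, and the choice is the sponsor's:

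- Reverse-code item 16 (5 minus response) and declare that lower is better. The summed total runs from 12 (fully adherent) to 48.
- Reverse-code items 5 to 15, leave item 16 as it is, and keep higher as better. A fully adherent patient then scores 11 × 4 + 4 = 48 and a fully non-adherent one 11 × 1 + 1 = 12.

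Say also whether the score is a sum or a mean. As a clarification of wording, list the subscale items by number in section 5.3.1 and its instrument table: refill 7, 8, 15 and 16; taking 5, 6 and 9 to 14.

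The cost is a few lines of text. The questionnaire, visits and sample size do not change.
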